4.2.5 Secondary outcome variables

Analyses of secondary outcome variables will handle intercurrent events as per the primary estimand, unless otherwise stated.

4.2.5.1 Time to first COPD exacerbation

Time to first COPD exacerbation over the 52-week treatment period will be analysed to explore the extent to which treatment with tezepelumab delays the time to first exacerbation compared to placebo. A Cox proportional hazard model will be fitted to the data with covariates of treatment, region and number of exacerbations recorded at randomization in IWRS (2, ≥ 3). Results will be summarised as hazard ratio for tezepelumab versus placebo with the 95% CI and p-value.

Time to first COPD exacerbation will also be displayed graphically using a Kaplan-Meier plot.

The number of subjects who are exacerbation free up to Week 52 will be summarised for each treatment group together with the censoring rate. The time to first exacerbation up to Week 52 will be summarised by minimum, maximum and percentiles (25th, median, 75th) with their corresponding 95% CIs using Kaplan-Meier technique. The probability of exacerbation free by Week 24 and Week 52 and their 95% CI, estimated using the Kaplan-Meier technique, will also be reported.

4.2.5.2 Proportion of subjects exacerbation free at Week 52

The proportion of subjects exacerbation free at Week 52 in the tezepelumab group will be compared to the proportion in the placebo group using a logistic regression model with region and number of exacerbations recorded at randomization in IWRS (2, ≥ 3) as covariates.

The results of the analyses will be presented as an odds ratio, together with associated 95% CI and 2-sided p-value. The number and percentage of subjects exacerbation free at Week 52 will also be summarised by randomised treatment group for subjects in the FAS.

4.2.5.3 Annual rate of severe COPD exacerbations

Annual rate of severe COPD exacerbations up to Week 52 will be analysed using a similar negative binomial model as outlined for the primary efficacy variable in Section 4.2.4.1 under the primary estimand only (for handling of intercurrent events) and with additional sensitivity analyses to assess the robustness of the results to missing data as outlined in Appendix 8.2.

The annual severe COPD exacerbations rate and the corresponding 95% CI within each treatment group will be presented. The estimated treatment difference from placebo (i.e. the absolute difference between tezepelumab and placebo, and the rate ratio of tezepelumab versus placebo), corresponding 95% CI, and 2-sided p-value for the ratio will be presented. Marginal standardisation methods will be used on the model estimates for all negative binomial analyses, unless otherwise specified.

If any notable differences in treatment effect are seen by subgroups for the primary endpoint, analyses of severe exacerbations in those subgroups may be conducted.

4.2.5.4 Time to first severe COPD exacerbation

Time to first severe COPD exacerbation through Week 52 will be analysed using a similar model for time to first COPD exacerbation as in Section 4.2.5.1.

4.2.5.5 Change from baseline in pre-dose/pre-BD FEV₁ (L) at Week 52

Change from baseline in pre-dose/pre-BD FEV₁ (L) at Week 52 will be compared between tezepelumab and placebo using a repeated measures analysis on subjects with a baseline pre-dose/pre-BD FEV₁ (L) and at least one non-missing post-randomisation pre-dose/pre-BD FEV₁ (L) value for subjects in the FAS. The dependent variable will be the change from baseline in pre-BD FEV₁ (L) at post-baseline protocol-specified visits (up to the EOT visit). Treatment group will be fitted as the explanatory variable, while region, prior exacerbation count as recorded in IWRS (2, ≥3), visit, baseline pre-dose/pre-BD FEV₁ (L), and the interaction between visit and treatment will be fitted as covariates. Visit will be fitted as a categorical variable, subject will be included in the model using the REPEATED statement (not the RANDOM statement), and the variance-covariance matrix will be assumed to be unstructured. If the procedure does not converge then a compound symmetric variance covariance matrix will be used instead. If the procedure fails to converge with both variance-covariance matrices above, then drop out of covariates will be considered. The Kenward-Roger method will be used in the model to calculate the denominator degrees of freedom, i.e. DDFM=KR. The model is:

*Change in pre-dose/pre-BD FEV₁ (L) = Treatment group + baseline pre-dose/pre-BD FEV₁ (L) + region + prior exacerbation strata + visit + treatment*visit*

This model will be used in two separate Mixed Model Repeated Measures model (MMRM) analyses [assuming missing at random (MAR)], namely:

- The primary analysis will handle intercurrent events as per the primary estimand.
- The supplemental analysis will handle intercurrent events as per the supplemental estimand.

Results will be presented in terms of LSMEANS (with the OBSMARGIN option added), treatment differences in LSMEANS, 95% CI, and p-values for all visits.

Summary statistics of the change from baseline in pre-dose/pre-BD FEV₁ (L) at the study site will be produced by treatment group and visit.

Additional sensitivity analyses to assess the robustness of the repeated measures analysis for pre-dose/pre-BD FEV₁ to missing data are outlined in Appendix 8.2.

Subgroup analyses of the change from baseline in pre-dose/pre-BD FEV₁ will be conducted for the subgroup factors listed in Section 3.1.7 based on FAS. The analyses will use the same MMRM model described above with additional terms for the subgroup main effect and the interaction among treatment, subgroup and visit. The model of each subgroup will be:

*Change in pre-dose/pre-BD FEV₁ (L) = Treatment group + baseline pre-dose/pre-BD FEV₁ (L) + region (if not subgroup) + prior exacerbation strata (if not subgroup) + visit + treatment*visit + subgroup + treatment* subgroup + subgroup* visit + treatment* subgroup*visit*

Region and prior exacerbation count at randomisation are not included as a covariate if they are the subgroup factor of interest. Imbalanced subgroups which cause convergence issues may be excluded from the analysis.

Similar outputs will be presented for each subgroup as for the change from baseline in pre-dose/pre-BD FEV₁ (L). The p-value for the interaction term by each treatment group will be presented in the summary tables and a forest plot will present the difference in LSMEANS with 95% CI intervals for each level of the subgroups.

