The E-RS: COPD is an 11-item PRO developed to evaluate the severity of respiratory symptoms of COPD ([Sexton et al 2010](#), [Sexton et al 2011](#)). The E-RS: COPD is a subset of items from the EXACT-PRO. The E-RS: COPD was designed to be captured as part of the daily EXACT-PRO assessment. Summation of E-RS: COPD item responses produces a total score ranging from 0 to 40, with higher scores indicating greater severity. In addition to the total score, symptom domain scores can be calculated for breathlessness (5 items; score range: 0–17), cough and sputum (3 items; score range: 0–11) and chest symptoms (3 items; score range: 0–12) by summing the responses of items within a respective domain. As with the total score, higher domain scores indicate greater severity.

Individual daily E-RS: COPD total and domain scores will be calculated and summarised as biweekly (14 days) means, derived by the following rules:

The biweekly mean is calculated as the sum of all non-missing daily measures/scores over 14 sequential days divided by the number of non-missing daily measures/scores. If more than 7 -daily measures/scores (>50%) within that period are missing, then the mean daily measure/score for that period is set to missing.

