4.2.6 Exploratory outcome variables

All continuous exploratory endpoints will be summarised descriptively and analysed under a MAR assumption using an MMRM model analogous to that specified for the secondary endpoints in Section 4.2.5.5 and handling intercurrent events as per the primary estimand.

The following is proposed for the exploratory endpoints:

- Change from baseline and percent change from baseline in blood eosinophil and neutrophil levels summarised descriptively
- Change from baseline in post-BD FEV₁ (L) analysed using MMRM and summarised descriptively
- Change from baseline in E-RSTM: COPD total score and domain scores analysed using MMRM and summarised descriptively
- Change from baseline in FENO analysed using MMRM and summarised descriptively

Results of MMRM analyses will be presented in terms of LSMEANS (with the OBSMARGIN option added), treatment differences in LSMEANS, 95% CI, and p-values for all visits.

Summary statistics of the EXACT-PRO event frequency, duration, and severity will be produced by treatment group.

Annual rate of EXACT-PRO defined exacerbation will be analysed using the method described for the primary analysis in Section 4.2.4.1 for subjects in the full analysis set. 95% CI will be presented for annual exacerbation rate, absolute difference, and the rate ratio.

All time to event exploratory endpoints will be analysed by using the same Cox proportional hazard model as in Section 4.2.5.1, and will be displayed graphically using a Kaplan-Meier plot.

This analysis includes the following endpoints:

- Time to first COPDCompEx event over 12-weeks
- Time to CID event over 52 weeks-treatment

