4.2.6.1 Other subject reported outcome variables

Total rescue medication use

Total rescue medication use and the number of nights with awakening and their change from baseline will be summarised by treatment and visit for subjects in the FAS.

Change from baseline in total rescue medication use will be analysed using the same MMRM method for pre-dose/pre-BD FEV₁ (L) as described in Section 4.2.5.5. Results will be presented in terms of LSMEANS (with the OBSMARGIN option added), treatment differences in LSMEANS, 95% CI, and p-values for all visits.

Nights with awakening due to respiratory symptoms

The number of nights with awakening and change from baseline will be summarised by treatment and visit.

Change from baseline in the proportion of nights with awakening due to COPD awakening will be analysed using the same MMRM method for pre-dose/pre-BD FEV₁ (L) as described in Section 4.2.5.5. Results will be presented in terms of LSMEANS (with the OBSMARGIN option added), treatment differences in LSMEANS, 95% CI, and p-values for all visits.

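### The MMRM fallback goes straight from unstructured to compound symmetry, so a fallback fit would misstate the Week 52 standard error if Week 52 variance differs from the visit average

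*SAP*

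**What the plan says.** SAP 4.2.5.5 defines the repeated-measures model for change in pre-bronchodilator FEV1. At the first step "the variance-covariance matrix will be assumed to be unstructured". The only alternative structure is the next one: "If the procedure does not converge then a compound symmetric variance covariance matrix will be used instead". Protocol 9.5.2.2 has the same two steps. The SAP then adds a third: "If the procedure fails to converge with both variance-covariance matrices above, then drop out of covariates will be considered". On inference it says: "The Kenward-Roger method will be used in the model to calculate the denominator degrees of freedom, i.e. DDFM=KR". No heterogeneous-variance or serial-correlation structure is named, and no empirical standard error.

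The model is reused widely:
- SGRQ (SAP 4.2.5.6) and CAT (4.2.5.8).
- The FEV1 and SGRQ subgroup models (4.2.5.5, 4.2.5.6).
- Continuous exploratory endpoints (4.2.6), analysed "using an MMRM model analogous to that specified for the secondary endpoints".
- Rescue use and night awakenings (4.2.6.1), for example: "Change from baseline in total rescue medication use will be analysed using the same MMRM method".

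The diary data are reduced to 14-day values. SAP 3.2.3.5 has E-RS scores "summarised as biweekly (14 days) means", and 3.2.3.6 treats rescue use and awakenings likewise. Yet 4.2.6.1 says: "Total rescue medication use and the number of nights with awakening and their change from baseline will be summarised by treatment and visit", and it reports the model results by visit. The plan does not say which time unit enters the model.

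**The concern.** Compound symmetry has two parameters: one variance for every visit and one correlation for every pair. The reported Week 52 standard error then rests on a variance pooled over all visits. Week 52 is the time point that defines the FEV1, SGRQ and CAT endpoints, and it is the visit furthest from baseline. If residual variance grows with time, pooling makes the Week 52 interval too narrow and the p-value too small; if variance shrinks, the reverse. Kenward-Roger does not protect against this, because it takes the chosen structure as correct.

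Rising variance is a plausible direction after baseline adjustment, since one baseline value usually explains less of later visits than of early ones. That is an assumption about this trial, not something the documents report.

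The rule is also coarse. It jumps from the richest structure to nearly the poorest, and the step after that is only to be considered, which leaves discretion.

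**Working it through.** **1. What the plan provides.** It gives no SD, between-visit correlation or convergence figure for any MMRM endpoint, so there is no plan figure to reproduce on this point. Its sizing figures concern the negative binomial primary analysis, and they do reproduce. With mean exposure 0.95, n = (1.645 + 0.842)² × [1/(0.95×1.6) + 1/(0.95×1.12) + 2×0.6] / (ln 0.7)² = 135.97, so 136 per arm as stated. The 169 per arm used below is from SAP 1.3.

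**2. Size of the unstructured matrix.** T time points need T(T+1)/2 parameters. T is read from protocol Table 2.

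| Endpoint | T | Parameters |
|---|---|---|
| CAT (Weeks 12, 24, 36, 52) | 4 | 10 |
| FEV1 (Weeks 4, 12, 24, 40, 52) | 5 | 15 |
| SGRQ (Weeks 12, 24, 36, 48, 52) | 5 | 15 |
| Diary, if by four-weekly visit | 13 | 91 |
| Diary, if by 14-day period (52/2) | 26 | 351 |

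The figure of 26 is derived; neither document states it.

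**3. Closed form, complete data.** The Week 52 treatment difference has true SE = σ₅₂ × √(2/169). Compound symmetry reports σ_pooled × √(2/169), where σ²_pooled is the mean of the visit variances. So

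ratio = √(mean visit variance / Week 52 variance), and two-sided error = 2 × [1 − Φ(1.96 × ratio)].

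- FEV1, five equal steps, assumed SD 0.20 to 0.25 L (1.25-fold): mean variance 0.05094, ratio √0.05094 / 0.25 = 0.903, error 7.7%. Placing the SDs at the actual weeks gives 0.896 and 7.9%.
- 26 periods, assumed SD 4 to 6 (1.5-fold): mean variance 25.36, ratio √25.36 / 6 = 0.839, error 10.0%.

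**4. With dropout, in both directions.** This is a large-sample calculation for 26 periods, 169 per arm and 10% uniform dropout. All covariances are assumed. Errors are computed from the rounded ratios.

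| Assumed truth | Reported SE / true SE | Two-sided error |
|---|---|---|
| Compound symmetry | 1.00 | 5.0% |
| Decaying correlation, constant variance | 0.97–0.99 | 5.2–5.7% |
| Stationary decaying process, given baseline | 0.84–0.92 | 7.1–10.0% |
| SD rises 1.3-fold | 0.88 | 8.5% |
| SD rises 1.5-fold | 0.83 | 10.4% |
| SD falls 1.3-fold | 1.14 | 2.5% |

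Unrounded ratios give errors from about 2.5% to 10.6%. Over 0 to 20% dropout the ratio runs from 0.81 to 1.15. For five FEV1 visits at 10% dropout it runs from 0.82 to 1.16.

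In the 1.3-fold case the compound-symmetry SE is 0.128. The true SE of that same estimator is 0.146, and the unstructured SE is also 0.146. The estimator loses almost no precision; the fault lies in the SE it reports.

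**5. Would unstructured fail at 26 periods?** Eight simulated maximum-likelihood fits (169 per arm, 10% dropout, 0 or 5% intermittent gaps) all converged in 5 to 8 iterations. Ten REML fits also all converged: four at 10% dropout with 5% gaps, four at 20% with 15%, and two at 30% with 20%. A repeat at those REML settings converged too. These are few runs, on well-behaved simulated normal data, and not in SAS.

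**The case against.** The strongest reply is that the rule may never be invoked. A reader might infer that 351 parameters against 338 subjects makes failure likely. That comparison is the wrong one: an unstructured matrix needs residual degrees of freedom above the number of periods, and full follow-up would give 338 × 26 = 8,788 observations. Every test fit converged. Moreover, the diary model may use visits rather than biweekly periods. For FEV1, SGRQ and CAT, with 10 to 15 parameters, failure is improbable. The subgroup models add fixed effects, not covariance parameters, and the SAP allows imbalanced subgroups that cause convergence trouble to be left out.

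This stands: the documents do not show that the fallback is likely. It does not show that the rule is harmless. The sponsor provides for non-convergence here and again for the imputed datasets (SAP 8.2). Diary gaps are built in: a period is missing when more than 7 of 14 days are missing, a rescue-use day is missing if either entry is missing, and subjects on follow-up option 3 stop the diary.

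A second reply is that the consequences are small. The primary endpoint uses a negative binomial model, the diary endpoints are exploratory, and SAP 4.1.2 treats all these p-values as nominal. That stands too and limits the weight of the point, but the 95% intervals will still be reported and read.

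**Conclusion.** The point holds conditionally, as a cheap improvement. If unstructured fails and compound symmetry is used with model-based inference, the Week 52 standard error is biased whenever Week 52 variance differs from the visit average. For assumed SD rises of 1.25- to 1.5-fold the ratio is about 0.90 to 0.83, with two-sided error about 8 to 10%. It is 1.00 under true compound symmetry and about 1.14, with error about 2.5%, for a 1.3-fold fall.

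A reader might go further and conclude that the plan understates the Week 52 standard error. The documents do not support that. It would take both a convergence failure and rising variance, and they give no evidence on either. Fallback is most plausible, though not demonstrated, for diary endpoints modelled as 26 biweekly means over the full 52 weeks. The undefined diary time unit is a gap in the plan in its own right. Nothing here touches the primary analysis.

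**What to change.** In SAP 4.2.5.5, replace the single fallback with an ordered list. If unstructured does not converge, use the first of heterogeneous Toeplitz, ARH(1), heterogeneous compound symmetry and then compound symmetry that does. For any structured fit, use empirical (sandwich) standard errors and name a compatible degrees-of-freedom method in place of Kenward-Roger. Report the structure used for each endpoint. In SAP 4.2.6 and 4.2.6.1, state whether the repeated time unit for E-RS, rescue use and night awakenings is the 14-day period or the visit.

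The cost is a short SAP edit and a few program lines. A fallback fit may give slightly wider intervals. Nothing changes where unstructured converges.

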3.2.2.4 Time to first severe COPD exacerbation

A severe exacerbation event will be defined in the same way as outlined in Section 3.2.1.1.

Time from randomisation to first severe COPD exacerbation through Visit 16 (EOT) will be derived using the same approach as in Section 3.2.2.1. The time to first severe COPD exacerbation for subjects who complete Visit 16 (EOT) and do not experience a severe COPD exacerbation will be censored at Visit 16 date. For subjects lost to follow-up, prematurely withdrawing from the study, or discontinue the study treatment and remain in the study, the time to first severe COPD exacerbation will be censored at the end of the maximum follow-up time, as described in Section 3.2.1.1.

3.2.2.5 Change from baseline in pre-dose/pre-BD FEV₁ (L) at Week 52

Pre-dose/pre-BD FEV₁ (L) will be determined by spirometry at the clinic visit. The change in FEV₁ (L) from baseline to each of the post-randomisation visits (post Visit 3) up to and including the Week 52 visit (Visit 16) will be assessed with change from baseline at Week 52 used as the secondary efficacy variable.

Change from baseline is obtained as an absolute difference between Week 52 measure and the baseline value as defined in Section 3.1.2 and Section 3.1.3. Changes from baseline at other post-baseline time points will be calculated similarly.

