4.2.5.6 St. George's Respiratory Questionnaire (SGRQ)

Changes from baseline in SGRQ total score at Week 52 will be analysed using a similar model (MMRM) for change from baseline in pre-dose/pre-BD FEV₁ (L) in Section 4.2.5.5, with the appropriate baseline value used in the model.

Results will be presented in terms of LSMEANS (with the OBSMARGIN option added), treatment differences in LSMEANS, 95% CI, and p-values for all visits. The results at Week 52 will be of primary interest.

The individual component scores and SGRQ total scores and changes from baseline will be summarised by treatment group and visit.

The cumulative distribution function of absolute changes from baseline in SGRQ total score at Week 52 will be also plotted in a figure.

The proportion of subjects in terms of SGRQ total score response status (improvement, worsening, no change, and not evaluable) at Week 52 will be summarised descriptively by treatment group.

Additional sensitivity analyses to assess the robustness of the repeated measures analysis for SGRQ to missing data are outlined in Appendix 8.2.

Subgroup analyses of the change from baseline in SGRQ total score will be conducted for the subgroup factors listed in Section 3.1.7 based on FAS. The analyses will use the same MMRM model described in Section 4.2.5.5 with additional terms for the subgroup main effect and the interaction among treatment, subgroup and visit. The model of each subgroup will be:

*Change from baseline in SGRQ total score = Treatment group + baseline SGRQ + region (if not subgroup) + prior exacerbation strata (if not subgroup) + visit + treatment*visit + subgroup + treatment* subgroup + subgroup* visit + treatment* subgroup*visit*

Region and prior exacerbation count are not included as a covariate if they are the subgroup factor of interest. Imbalanced subgroups which cause convergence issues may be excluded from the analysis.

Similar outputs will be presented for each subgroup as for the change from baseline in SGRQ total score. The p-value for the interaction term by each treatment group will be presented in the summary tables and a forest plot will present the difference in LSMEANS with 95% CI intervals for each level of the subgroups.

4.2.5.7 Proportion of subjects achieving a decrease of ≥ 4 -points in SGRQ total score at Week 52 (MCID)

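### The single interaction p-value planned for the FEV1 and SGRQ subgroup analyses is not tied to Week 52, and neither model term it could refer to tests a Week 52 subgroup difference

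*SAP*

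**What the plan says.** SAP 3.2.2.5 fixes the time point for FEV1: the change from baseline at each visit "will be assessed with change from baseline at Week 52 used as the secondary efficacy variable". For SGRQ, SAP 4.2.5.6 says: "The results at Week 52 will be of primary interest".

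The main model in SAP 4.2.5.5 uses every post-baseline visit, with visit categorical, and "the variance-covariance matrix will be assumed to be unstructured". By Protocol Table 2, the post-baseline visits are Weeks 4, 12, 24, 40 and 52 for FEV1 and Weeks 12, 24, 36, 48 and 52 for SGRQ.

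For each factor in SAP 3.1.7 the subgroup model gains "additional terms for the subgroup main effect and the interaction among treatment, subgroup and visit". The model equations in both sections list a treatment×subgroup term and a treatment×subgroup×visit term. Both sections then give the same reporting sentence: "The p-value for the interaction term by each treatment group will be presented in the summary tables". A forest plot of the least squares mean differences by subgroup level is also promised, without a visit.

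**The concern.** The subgroup question for an endpoint defined at Week 52 is whether the Week 52 treatment difference is the same at every level of the factor. The SAP promises one p-value from a model with two candidate terms, and as ordinary model-term tests neither candidate answers that question. The reporting sentence matches the one in SAP 4.2.4.3 for the exacerbation rate. It works there because that model has only one treatment-by-subgroup interaction and no visit dimension.

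SAP 3.1.7 lists 15 factors, including eosinophils, FeNO, bronchitis and emphysema, and smoking. All are run on both endpoints, which makes 30 such p-values. Protocol 9.5 says the results at primary database lock will feed Phase 3 design. A p-value printed beside Week 52 estimates will be read as a Week 52 test. If it is not one, a subgroup difference at Week 52 can be overlooked, or a difference confined to earlier visits can be taken as heterogeneity at Week 52.

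**Working it through.** **No plan figure for these tests.** The documents state no power for the FEV1 or SGRQ subgroup interactions. The sample size calculation concerns the exacerbation rate and enters here only through N = 338, 169 per arm. Its stated 136 per arm does reproduce, with mean follow-up 0.95 for 10% uniform drop-out: (1.645+0.842)² × [(1/0.95)(1/1.6+1/1.12) + 2×0.6] / ln(0.7)² = 135.97.

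**What each term tests.** For a two-level factor, let d_v be the difference between levels in the treatment effect at visit v, over five visits.

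- Week 52 contrast: d_52 = 0 (1 df).
- Treatment×subgroup, Type 3 with the three-way term in the model: (sum of d_v)/5 = 0 (1 df). Week 52 carries one fifth of the weight.
- Treatment×subgroup×visit: all d_v equal (4 df). A difference of any size that is the same at every visit satisfies this null.

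**Assumptions (not in the documents).** Complete data, two-sided 5%, equal SD at each visit, exchangeable correlation ρ of 0.5, 0.7 or 0.85, and a 50/50 subgroup split.

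**Size of the Week 52 interaction.** In SD units, SE = √{2[1/84.5 + 1/84.5]} = 0.218. An interaction of (1.960+0.842) × 0.218 = 0.61 SD gives the Week 52 contrast 80% power. At a 20/80 split, SE = √{2[1/33.8 + 1/135.2]} = 0.272 and the interaction is 0.76 SD. Scaled this way, the table below is the same for both splits.

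**Formulas.** With δ = 2.802 (the Week 52 difference divided by its SE) and visit pattern w_v:

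- two-way term: z = δ × mean(w) / √[(1+4ρ)/5];
- three-way term: non-centrality = δ² × Σ(w_v − mean w)² / (1−ρ), on 4 df.

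Example, difference at Week 52 only, ρ = 0.5. Two-way: z = 2.802 × 0.2 / √0.6 = 0.72, power 11%. Three-way: 7.85 × 0.8 / 0.5 = 12.6, power 82%.

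**Probability of rejection (ρ = 0.5 / 0.7 / 0.85).**

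| Pattern of subgroup difference | Week 52 contrast | Treatment×subgroup | Treatment×subgroup×visit |
|---|---|---|---|
| None at any visit | 5% | 5% | 5% |
| Same at every visit | 80% | 95 / 90 / 85% | 5% |
| Growing linearly to Week 52 | 80% | 45 / 37 / 33% | 67 / 89 / 100% |
| Late (0, 0, 0, ½, 1) | 80% | 19 / 16 / 15% | 82 / 97 / 100% |
| Week 52 only | 80% | 11 / 10 / 9% | 82 / 97 / 100% |
| Early, zero at Week 52 (1, 1, 1, ½, 0) | 5% | 72 / 61 / 55% | 82 / 97 / 100% |

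The linear row uses the FEV1 weeks. Under exchangeable correlation the other rows depend only on there being five visits in that order, so they also describe SGRQ. A correlation that decays with time (FEV1 weeks, 0.7 per 24 weeks) gives the same picture: for the constant pattern, 89% two-way and 5% three-way; for Week 52 only, 10% two-way.

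**Checks by simulation (4,000 runs).** At ρ = 0.7, Week 52 / two-way / three-way: constant 78/89/4%, Week 52 only 80/10/97%, early only 5/59/97%. A separate simulation fixed the interaction at 0.6 SD, with ρ = 0.4, ρ = 0.6 and a decaying structure. For a constant difference it gave 78–79% for the Week 52 contrast, 87–97% two-way and 4–5% three-way. For a late difference the two-way term had 16–21%. For an early-only difference the two-way term rejected in 59–75% and the three-way in 72–89%.

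**The case against.** **The text does not commit to a wrong term.** A reader might infer that the three-way term is what will be reported, because the SAP describes the added interaction as involving visit. The SAP never says so. The sentence repeats the wording of 4.2.4.3, where it means treatment×subgroup, so the two-way reading is at least as likely. Under that reading a constant difference is detected with 85–95% power in the table, better than the Week 52 contrast. This stands, and the harm must be stated as conditional on the term.

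**A Week 52 test is compatible with the text.** The subgroup outputs are to resemble the main ones, which are given at every visit. Under default SAS reference coding with Week 52 as the last visit, the treatment×subgroup coefficient for a two-level factor would be the Week 52 contrast. This stands as a possibility only. No passage asks for it, it would come about by accident of coding, and it would not serve the factors with three or four levels.

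**The off-target rejections are not false positives in the usual sense.** A reader might infer inflated type I error. All three tests hold 5% when there is no interaction at any visit. The early-only rejections are real differences at earlier visits and are misleading only when read as Week 52 findings.

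**The illustration is favourable.** Neither 0.6 SD nor the 50/50 split comes from the documents. With an interaction of 0.3 SD (0.3/0.218 = 1.38) the Week 52 contrast has about 28% power. At a 20/80 split it has about 60% for 0.6 SD and 20% for 0.3 SD. The contrast puts the question on target; it does not make these analyses well powered.

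**Little rides on the p-values.** SAP 4.1.2 makes every p-value beyond the primary test nominal, no decision rule uses these, and subgroup estimates with 95% intervals are shown regardless. This limits the severity but does not supply the missing test.

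**Conclusion.** The point holds in conditional form. SAP 4.2.5.5 and 4.2.5.6 leave the term and visit of the reported p-value undefined, and neither candidate term, as an ordinary Type 3 test, addresses the Week 52 endpoint. If the three-way term is used, a constant subgroup difference is invisible (5%, against 80% for the contrast). If the two-way term is used, a late or Week 52-only difference is mostly missed (9–19% in the table, up to 21% in simulation), while a constant one is found more readily than by the contrast. Either term often rejects for an early difference that is absent at Week 52 (55–75% two-way, 72–100% three-way, across all settings run).

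These figures rest on assumed correlations, complete data, a two-level factor and an interaction of about 0.6 SD; factors with more levels were not calculated. The documents do not support the stronger conclusions that the SAP has chosen the wrong term, that error rates are inflated when there is no interaction at any visit, or that any trial conclusion is endangered. The primary-endpoint subgroup test is unaffected. The change should still be made, because it is almost free and settles the choice for 30 analyses in advance.

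**What to change.** In SAP 4.2.5.5 and 4.2.5.6:

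1. Define the reported p-value as the test, from the same fitted model, that the Week 52 treatment difference is equal across subgroup levels, with (number of levels − 1) numerator df and Kenward-Roger denominator df.
2. State that the forest plot shows Week 52 least squares mean differences, with this p-value beside them.
3. Drop the qualifier that attaches the p-value to each treatment group, here and in SAP 4.2.4.3. A two-arm trial has one interaction test per factor.

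The model stays as written. The cost is a sentence or two in each section and one contrast statement per model. No new data and no protocol amendment are needed, since Protocol 9.5.3 leaves subgroup detail to the SAP. The downside is somewhat lower power than the visit-averaged term if the subgroup difference is constant over time (80% against 85–95% in the table). If that average is also of interest, it can be shown as a labelled supplementary result.
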